9.7.1.4 Demographic and Other Baseline Characteristics

Demographic and other baseline characteristics for the Safety Analysis Set and FAS will be summarized for each treatment group using descriptive statistics. Continuous demographic and baseline variables include age, CDR scores, ADAS-cog14, MMSE and FAQ; categorical variables include sex, age group (equal or less than 65 years, age greater than 65 years), race, ethnicity, region, *ApoE4* genotype, prior treatment with AChEIs or memantine (no or yes), and clinical subpopulation (MCI due to AD or the early stages of mild AD).

9.7.1.5 Prior and Concomitant Therapy

All investigator terms for medications recorded in the eCRF will be coded to an 11-digit code using the World Health Organization Drug Dictionary (WHO DD) (Mar 2014). The number (percentage) of subjects who took prior and concomitant medications will be summarized on the Safety Analysis Set by treatment group, Anatomical Therapeutic Chemical class, and WHO DD preferred term (PT). Prior medications will be defined as medications that stopped before the first dose of study drug. Concomitant medications will be defined as medications that (1) started before the first dose of study drug and were continuing at the time of the first dose of study drug, or (2) started on or after the date of the first dose of study drug up to the date of the last dose. All medications will be presented in subject data listings.

Medications taken within the 12-week Follow-up Period will also be recorded.

9.7.1.6 Efficacy Analyses

The FAS will be used as the primary population for all efficacy analyses, while the PPS will be used as the supportive population.

9.7.1.6.1 PRIMARY EFFICACY ANALYSIS

The primary analysis will be based on an intent to treat philosophy without regard to adherence to treatment. The primary analysis of the change from baseline in CDR-SB at 24 months will be performed to compare elenbecestat 50 mg per day versus placebo using a linear mixed effects model for repeated measures (MMRM) on the FAS. The MMRM model will include fixed effects of treatment group, visit, treatment group by visit interaction, baseline CDR-SB, baseline CDR-SB by visit interaction, and randomization stratification variables (ie, region [7 levels], clinical dementia [yes, no], and concurrent AD medication use at randomization [Visit 2] [yes, no]). *ApoE4* status may be included in the model if appropriate. (revised per Amendment 05) An unstructured covariance matrix will be employed to model the covariance of within subject effect; if MMRM fails to converge then a covariance structure with fewer parameters from the following list will be employed according to the prespecified order in the list until the MMRM converges. The list of covariance structure will include Heterogeneous Toeplitz, Toeplitz, Heterogeneous Compound Symmetry, and Compound Symmetry. This primary analysis will include all observed post baseline data of the change from baseline in CDR-SB without imputation of missing values. The treatment effect for elenbecestat versus placebo will be compared at

24 months based on MMRM model. The LS means and difference in LS means between elenbecestat treatment group and placebo, and corresponding 95% CI will be presented.

The null hypothesis is that there is no difference in the mean change from baseline in CDR-SB at 24 months between elenbecestat 50 mg per day and placebo. The corresponding alternative hypothesis is that there is a difference in the mean change from baseline in CDR-SB at 24 months between elenbecestat 50 mg per day and placebo.

The primary analysis will be repeated to minimize the impact of change in concomitant AD medications where efficacy data after initiation of new AD medications and increase of current AD medications will be censored.

The following sensitivity analysis will be conducted to evaluate the impact of missing data: the primary endpoint will be analyzed using ANCOVA after multiple imputation. The ANCOVA model will include baseline CDR-SB as a covariate, with treatment group and randomization stratification variables as factors. *ApoE4* status may be included in the model if appropriate. Additional sensitivity analyses will be performed to assess the robustness of the missing at randomization assumption in the primary MMRM model.

Subgroup analysis (eg, stratification factors and *ApoE4* status) and additional sensitivity analysis for the primary endpoint will be performed as appropriate. (revised per Amendment 05)

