9.7.1 Statistical and Analytical Plans

All statistical analyses will be performed by the Sponsor or designee after the study is completed and the database is locked and released for unblinding. All statistical analyses will be performed based on the pooled data from 2 studies (E2609-G000-301 and E2609-G000-302). The analyses will also be performed within each study to confirm the trend of the efficacy and biomarker endpoints unless specified. (revised per Amendment 05)

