9.7.1.1 Study Endpoints

9.7.1.1.1 PRIMARY ENDPOINT

The primary endpoint of the study is:

- Change from baseline in the CDR-SB at 24 months in the combined studies (revised per Amendment 05)

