9.7.2 Determination of Sample Size

The sample size for this study is estimated for comparison of elenbecestat versus placebo with respect to a pooled analysis of studies E2609-G000-301 and E2609-G000-302 for the change from baseline in CDR-SB at 24 months. Based on the available data from the placebo group in Study BAN2401-G000-201 (a recently completed study with a comparable subject population), the mean and the standard deviation of the change from baseline in CDR-SB at 24 months in the placebo group are assumed to be 1.46 and 2.05, respectively, instead of 1.75 and 2.05, which are originally assumed by the available data from ADNI (of amyloid positive, MMSE equal or greater than 24, late MCI [global CDR=0.5, CDR memory box \geq 0.5]). Therefore, assuming a 25% reduction in the mean change from baseline CDR-SB at 24 months for elenbecestat compared to placebo with common standard deviation of 2.05 and 30% dropout rate, a total sample size of 1900 subjects, 950 subjects in each treatment group, will be required to detect the treatment difference between elenbecestat and placebo using a 2-sample t test with 90% power at a significance level of 2 sided alpha =0.05.

The pooled data from 2 studies (E2609-G000-301 and E2609-G000-302) will comprise the total sample size of approximately 1900 subjects. At least 850 subjects will be randomized in each study. (revised per Amendment 05)

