If the amyloid hypothesis is correct, inhibition of cerebral A β accumulation by inhibitors of BACE1 could benefit patients with AD by potentially lowering cerebral A β concentrations and thereby slowing the progression of cognitive decline. Unfortunately, early attempts to develop potent in vivo BACE1 inhibitors were not successful, mainly due to poor brain penetration (Sinha, et al., 1999). Recently, poor blood–brain barrier penetration has been overcome with the development of potent third-generation small-molecule BACE1 inhibitors that exhibit satisfactory pharmacokinetics (PK) and robust cerebral A β reduction in preclinical animal models. As a result of these progresses, several BACE1 inhibitors have entered clinical studies in humans.

Elenbecestat (E2609) is a novel, small-molecule BACE1 inhibitor. Preclinical studies have shown that after oral dosing, elenbecestat (E2609) inhibits the production of A β 40 and A β 42 in brain (rat and guinea pig) and in CSF and plasma (rat, guinea pig, and monkey). In humans, elenbecestat (E2609) has been shown to inhibit BACE enzyme activity in CSF thereby lowering CSF levels of amyloid β , including A β (1-x), A β (1-40), and A β (1-42), both in vitro and in vivo in single ascending dose (SAD) and multiple (14 days) ascending dose studies (Elenbecestat (E2609) Investigator’s Brochure). An ongoing study (study E2609-G000-202; Study 202) has yielded data in subjects with MCI due to AD /Prodromal AD and mild-to-moderate AD dementia (AD-D) administered oral doses of elenbecestat (E2609). Interim study data indicated measurable levels of the BACE1 inhibitor in the CSF as well as inhibition of BACE activity and reduction of various forms of A β (eg, 1-x, 40, 42) after daily administration for 4 weeks.

This clinical study, E2609-G000-302 (Study 302), is 1 of 2 studies in the Phase 3 elenbecestat (E2609) program, and is primarily designed to evaluate the efficacy, safety, and tolerability of elenbecestat (E2609) in subjects with Early Alzheimer’s Disease (EAD). Confirmation is also required that these subjects meet the NIA-AA core clinical criteria for MCI due to AD or Mild AD. This study is intended to be pivotal for registration and marketing for this patient population.

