9.4.3 Method of Assigning Subjects to Treatment Groups

Subjects will be assigned to treatments based on a computer-generated randomization scheme that will be reviewed and approved by an independent statistician. The randomization scheme and identification for each subject will be included in the final clinical study report for this study. The doses and number of treatment groups to be used are described in [Section 9.4.1](#).

Stratification and randomization will be performed centrally by an IxRS. The IxRS or clinical supply vendor will generate the randomized bottle identification numbers. At enrollment (Screening), the investigator or designee will call the IxRS to register the subject information. At randomization (Visit 2), the IxRS will assign each subject a unique randomization number.

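### The primary MMRM pools studies 301 and 302 but has no study term; the loss is small and conservative, and the term costs almost nothing to add

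*Protocol*

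**What the plan says.** All of this is in the current (Amendment 05) text of the protocol.

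- Section 9.7.1: "All statistical analyses will be performed based on the pooled data from 2 studies (E2609-G000-301 and E2609-G000-302"). Within-study analyses are planned as well, to confirm the trend.
- Section 9.7.1.1.1 gives the primary endpoint as "Change from baseline in the CDR-SB at 24 months in the combined studies".
- Section 9.7.2: "At least 850 subjects will be randomized in each study", within a pooled total of about 1900.
- Section 9.7.1.6.1: "The MMRM model will include fixed effects of treatment group, visit, treatment group by visit interaction, baseline CDR-SB, baseline CDR-SB by visit interaction", plus "randomization stratification variables (ie, region [7 levels], clinical dementia [yes, no], and concurrent AD medication use at randomization [Visit 2] [yes, no"]). Study is not named. On ApoE4, the same paragraph says that "status may be included in the model if appropriate".
- Section 9.7.1.6.1 (multiple-imputation ANCOVA) and Section 9.7.1.6.2 (slope model, two Cox models) adjust for the same stratification variables and do not name study. ADCOMS and amyloid PET SUVR reuse the primary MMRM.

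Amendment 05 did revise the fixed effects. The superseded text of Section 9.7.1.6.1, reproduced later in the same file, has neither the baseline-by-visit term nor the ApoE4 sentence. Study was not added in that revision, although it was the revision that moved the primary analysis to pooled data.

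**The concern.** When two studies that each randomise their own subjects are pooled for one confirmatory test, the treatment contrast should be formed within study and then combined. Leaving study out has two possible effects. Any difference between the studies in mean decline goes into the residual, which widens the standard error. And if the arms do not draw the same share of their Month 24 information from each study, for instance because dropout differs by arm and study, part of the between-study difference is counted as treatment effect. The primary test also gates the key secondary tests, two of which use the same model on the pooled data, so the omission carries through.

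**Working it through.** **Inputs from Section 9.7.2:** placebo mean change 1.46; common SD 2.05; 25% reduction; 30% dropout; 90% power; two-sided alpha 0.05; 1900 subjects, 950 per arm; at least 850 per study.

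**Assumptions, not in the documents:** the between-study difference D in mean 24-month change, and any imbalance of arms across studies. Both are shown as ranges.

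**1. The plan's own figure.** Difference = 0.25 × 1.46 = 0.365. Per arm, n = 2 × (1.960 + 1.282)² × 2.05² / 0.365² = 663. Dividing by 0.70 gives 948, total 1896. The t-test version gives 664, then 949, total 1898. The stated 1900 reproduces, so this point does not touch the sample size.

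**2. Standard error without study.** With studies of equal size the residual variance gains D²/4, so the inflation is √((2.05² + D²/4) / 2.05²) − 1.

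| D (points) | D²/4 | Inflation |
|---|---|---|
| 0.3 | 0.0225 | 0.3% |
| 0.5 | 0.0625 | 0.7% |
| 1.0 | 0.2500 | 2.9% |

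**3. Size and power.** Take 0.70 × 950 = 665 evaluable per arm and an 850/1050 split. The added variance is (850/1900) × (1050/1900) × D² = 0.247 D². With 1:1 allocation in each study, the true standard error of the difference is the within-study one (SD 2.05), while the test uses the inflated one. So alpha = 2 × [1 − Φ(1.96 × SE without / SE with)] and power = Φ((0.365 − 1.96 × SE without) / SE with).

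| D | SD used | Alpha | Power |
|---|---|---|---|
| study in model | 2.050 | 0.0500 | 90.1% |
| 0.25 | 2.054 | 0.0496 | 90.0% |
| 0.5 | 2.065 | 0.0483 | 89.8% |
| 1.0 | 2.109 | 0.0437 | 89.1% |

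A single-time-point simulation (no treatment effect, 595 and 735 evaluable subjects, 4000 runs per setting) agrees. The mean estimated difference stayed between −0.0015 and 0.0035. At D = 1.0 the rejection rate was 4.3% to 4.7% without study and 4.9% to 5.2% with it.

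**4. Unequal study mix.** Shift = D × (difference between arms in the share of data from the faster-declining study). Suppose 52% of subjects in the study of 850 and 48% in the study of 1050 are on active drug. The active arm then has 504/946 = 53.3% from the larger study and placebo has 546/954 = 57.2%, a gap of 4.0 percentage points. The shift is 0.010 points at D = 0.25, 0.020 at D = 0.5 and 0.040 at D = 1.0. That is about 3% to 11% of 0.365, in either direction. A gap of 5 points with D = 0.5 gives 0.05 × 0.5 = 0.025, or 6.8%.

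**The case against.** **The effect is close to nil.** With balanced allocation there is no bias, and the error in test size is on the safe side. Values of D from 0.5 to 1.0 are 34% to 68% of the assumed placebo decline of 1.46 (0.5/1.46 and 1.0/1.46), which is a lot for two studies that the protocol's change log calls identical. The imbalance in step 4 is hypothetical, and the MMRM uses every observed post-baseline visit, which should absorb part of any Month 24 imbalance. All of this stands and sets the size of the point. It is not a reason to leave study out.

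**The list need not be exhaustive.** It says what the model will include, and an SAP could add study. That is fair. But Amendment 05 rewrote this list while moving to pooled data, so the gap is in the text as fixed.

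**A reader might infer that the analysis ignores the randomisation.** The documents do not support that. All three named stratification factors are in the model. Study is a further, implicit stratum, inferred from Section 9.7.2 and from the Introduction of the superseded version, where this study "is 1 of 2 studies in the Phase 3 elenbecestat (E2609) program". No section describes separate randomisation lists.

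**A reader might also infer that the optional ApoE4 term leaves two primary models and an inflated type I error.** If both were fitted and the smaller p-value reported, two-sided alpha would be about 5.5% to 5.8%, with ApoE4 assumed to explain 1% to 3% of the variance. The protocol does not provide for such a choice, and an SAP normally settles a covariate of this kind before unblinding. The inflation is therefore not a property of this plan.

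**Conclusion.** The omission is real and worth correcting, but it does not threaten the validity of the primary test. With 1:1 allocation in both studies, the standard error is about 0.3% to 2.9% too wide for D from 0.3 to 1.0 points, alpha lies between 0.044 and 0.050, and power falls by at most about 1 percentage point. A shift arises only if the arms differ in study mix: about 0.01 to 0.04 points under the imbalance shown in step 4. D and the imbalance are assumptions, and the calculations treat Month 24 as a single time point, so they approximate the MMRM.

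The ApoE4 wording is a secondary matter of stating the choice in time; it does not carry the point.

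**What to change.** - **Pooled MMRMs** (CDR-SB, ADCOMS, amyloid PET SUVR and the other continuous endpoints): add study (301/302) and study-by-visit as fixed effects. The interaction is needed because a difference in rate of decline grows with time, and a constant study effect would not adjust fully at Month 24.
- **Multiple-imputation ANCOVA:** add study as a factor.
- **Slope model:** add study and study-by-time.
- **Cox models:** stratify by study.
- **ApoE4 (secondary):** state before unblinding whether it is in the primary model, and run the other version as a sensitivity analysis. If it is included, define a missing-genotype category so that no FAS subject is dropped; Appendix 4 allows for countries whose laws prohibit the sample.

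**Cost:** wording, and a few degrees of freedom. Table 5 schedules eight on-treatment CDR assessments after baseline (Visits 6 to 13), so the primary MMRM gains 1 + 7 = 8 fixed-effect parameters, against about 0.70 × 1900 = 1330 evaluable subjects.

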The CDR will be conducted every 3 months during the Core Study; other cognitive and functional assessment instruments will be administered every 6 months. Every 3 months, the investigator is required to confirm the clinical staging of AD (ie, dementia or nondementia). This staging decision will be verified via a central review process and adjudicated if necessary (adjudication will only occur when there is a discrepancy between the clinical disease staging made by the site compared to that determined by the central review process; moreover, where adjudication is required, it will be undertaken by an independent assessor(s)).

The health-related quality of life measures will be conducted every 6 months during the Core Study, along with the NPI-10.

MRI scans (including vMRI and fMRI) will be performed at 12 and 24 months during the Core Study or at the ED visit.

At every visit, AEs will be assessed, concomitant medications will be reviewed, physical examinations with dermatologic review by the study investigator will be performed, vital signs and respiratory rate will be measured, suicidality will be assessed, blood will be drawn for clinical chemistry, hematology, and for immunologic assessments. A urine sample will be provided for dipstick urinalysis. Other assessments, including safety assessments (neurologic exams, ECGs, urine pregnancy tests for females of child-bearing potential), and blood draws for PK, PD and assessment of immune status are performed at different intervals throughout the treatment period of the study.

For subjects who consent to the amyloid PET longitudinal substudy, amyloid PET will be conducted after 12 and 24 months of treatment during the Core Study (or at the ED visit, provided the subject has received at least 39 weeks of study drug and at least 6 months has elapsed since the prior amyloid PET scan was performed). (revised per Amendment 03) For subjects who consent to the CSF longitudinal substudy, CSF will be collected after 24 months of treatment during the Core Study (or at the ED visit, provided the subject has received at least 39 weeks of study drug). For subjects who consent to the tau PET longitudinal substudy, tau PET will be conducted at 24 months of treatment during the Core Study (or at the ED visit, provided the subject has received at least 39 weeks of study drug).

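### The primary MMRM's covariance fallback reaches common-variance Toeplitz before Heterogeneous Compound Symmetry, so in an unlikely double convergence failure the month-24 standard error could be too small

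*Protocol*

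**What the plan says.** Section 9.7.1.6.1 gives the first choice: "An unstructured covariance matrix will be employed to model the covariance of within subject effect". If that model does not converge, "a covariance structure with fewer parameters from the following list will be employed according to the prespecified order in the list until the MMRM converges". Its entries are, in sequence: "The list of covariance structure will include Heterogeneous Toeplitz, Toeplitz, Heterogeneous Compound Symmetry, and Compound Symmetry". So the order is fixed in the protocol itself and is not left to a later document.

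On inference the section says only: "The LS means and difference in LS means between elenbecestat treatment group and placebo, and corresponding 95% CI will be presented". It names no standard-error estimator and no degrees-of-freedom method.

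Section 9.1.2.1 sets the visit grid: "The CDR will be conducted every 3 months during the Core Study". That gives eight on-treatment assessments, months 3 to 24, as in the schedule of assessments. Section 9.7.2 gives the placebo mean and SD of change at 24 months, which "are assumed to be 1.46 and 2.05, respectively, instead of 1.75 and 2.05". No SD is stated for any earlier visit.

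**The concern.** Toeplitz and Compound Symmetry estimate a single variance for all visits. The primary contrast is at the last visit. If the variance of change is largest there, a common-variance structure averages it down with the earlier visits, and the model-based standard error of the month-24 difference comes out too small. Heterogeneous Toeplitz and Heterogeneous Compound Symmetry keep visit-specific variances and so largely avoid this, yet the second of them is listed after Toeplitz.

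The affected quantities would be the confirmatory p-value and the 95% CI. The primary test also opens the key secondary sequence (Section 9.7.1.6.2), so an understated standard error would carry forward.

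**Working it through.** **Plan's own figure.** The effect follows from "assuming a 25% reduction in the mean change from baseline CDR-SB at 24 months for elenbecestat compared to placebo": 0.25 × 1.46 = 0.365. With SD 2.05, two-sided alpha 0.05 and 90% power, n per arm = 2 × (1.960 + 1.282)² × 2.05² / 0.365² = 663 evaluable. Allowing for 30% dropout, 663 / 0.70 = 948, against the stated 950. The sample size reproduces and is not affected by this point.

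**Covariance parameters for K visits.** Unstructured K(K+1)/2; Heterogeneous Toeplitz 2K−1; Toeplitz K; Heterogeneous Compound Symmetry K+1; Compound Symmetry 2.

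- K = 8: 36, 15, 8, 9, 2.
- K = 4: 10, 7, 4, 5, 2.
- K = 2: 3, 3, 2, 3, 2.

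Every entry has fewer parameters than unstructured at K = 8, so the rule is not contradicted literally. But the list is not in descending order, since the third fallback has one parameter more than the second.

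**Size of the effect.** Inputs from the protocol: 8 visits, 950 per arm, 30% dropout, SD 2.05 at month 24. Assumptions: the SD path over earlier visits, the correlations, and dropout completely at random, spread evenly over visits. Each structure was fitted at its maximum expected likelihood. The model-based SE of the month-24 difference was then compared with its actual (sandwich) SE, and type I error = 2Φ(−1.96 × model SE / actual SE). For example, with SD rising from 1.0: 0.0766 / 0.1033 = 0.741, and 2Φ(−1.96 × 0.741) = 14.6%.

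| Assumed SD, month 3 to 24 | Toeplitz: model SE / actual SE | Ratio | Type I | Het. CS: ratio, type I |
|---|---|---|---|---|
| Flat 2.05 | 0.1021 / 0.1021 | 1.000 | 5.0% | 0.997, 5.1% |
| 1.5 to 2.05, linear | 0.0876 / 0.1024 | 0.855 | 9.4% | 0.997, 5.1% |
| 1.0 to 2.05, linear | 0.0766 / 0.1033 | 0.741 | 14.6% | 0.997, 5.1% |
| 0.8 to 2.05, linear | 0.0730 / 0.1038 | 0.703 | 16.8% | 0.997, 5.1% |
| Proportional to √t (0.72 at month 3) | 0.0745 / 0.1037 | 0.719 | 15.9% | 0.997, 5.1% |
| Random slope, residual SD 0.6 (0.88) | 0.0734 / 0.1025 | 0.716 | 16.1% | 0.946, 6.4% |
| Random slope, residual SD 0.8 (1.15) | 0.0792 / 0.1038 | 0.763 | 13.5% | 0.956, 6.1% |
| Random slope, residual SD 1.0 (1.43) | 0.0866 / 0.1047 | 0.827 | 10.5% | 0.969, 5.8% |

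The first five rows use a correlation of 0.85 × 0.95^(lag−1), with lag in visits.

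**The first fallback.** Heterogeneous Toeplitz is exact in the first five rows, whose correlation is Toeplitz by construction. Under random-slope data it is not: ratio 0.944 (6.4%) at residual SD 1.0, 0.903 (7.7%) at 0.8, 0.852 (9.5%) at 0.6, and 0.823 (10.7%) at 0.5, where the month-3 SD is 0.75. Reordering alone therefore does not fully protect the test; a sandwich SE would.

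**The case against.** Several objections stand and set the limits of the point.

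- A reader might infer that the protocol prescribes model-based standard errors. It does not; it is silent, and the estimator is ordinary SAP content. Silence is no defect here, and model-based SEs are a condition of the result. The order of the list, by contrast, is fixed in the protocol.
- A reader might infer that any use of the list is harmful in this way. The first fallback keeps visit-specific variances, so homogeneous Toeplitz is reached only after a 36-parameter and then a 15-parameter model have both failed with about 1900 subjects.
- Rising variance is an assumption. It is plausible: change is measured from each subject's own baseline, all enter at a global CDR of 0.5 (Section 9.3.1), and mean placebo change is taken to reach 1.46. But the protocol gives no early SD, and the bias vanishes if the SD is flat.
- A reader might infer that every secondary MMRM is affected alike. Amyloid PET has two scheduled on-treatment scans (Visits 9 and 13). With two time points, unstructured and both heterogeneous structures are the same 3-parameter model, so reordering changes nothing. ADAS-cog14, MMSE and FAQ have four on-treatment visits and only 10 unstructured parameters, so convergence is still less of a worry.
- The ANCOVA after multiple imputation in the same section does not use the fallback structure and would expose a suspiciously small SE, although it does not replace the primary p-value.

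The objections do not reach the order itself. A contingency rule is judged by what it does when invoked, and no advantage of this order is apparent. Non-convergence is also less remote in the analyses within each study (at least 850 subjects) and in the SUVR-enriched subset, where CDR-SB keeps eight visits on fewer subjects.

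**Conclusion.** The point holds in a limited form. The fixed order places an 8-parameter common-variance structure ahead of a 9-parameter structure with visit-specific variances. If unstructured and Heterogeneous Toeplitz both fail and SEs are model-based, the month-24 SE is about 14-30% too small and type I error is about 9-17%, assuming an SD rising from 0.8-1.5 to 2.05.

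These figures are conditional. They should not be read as the trial's type I error, because both failures are unlikely. Nor do they show that the point estimate is safe: the calculation took dropout as completely at random. If dropout depends on earlier scores, a misspecified covariance may also bias the estimate, which a sandwich SE would not repair.

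Starting from unstructured and fixing the order in advance are sound. The weakness is in the sequence, and the priority is low.

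**What to change.** Replace the list with: Heterogeneous Toeplitz, Heterogeneous Compound Symmetry, then Toeplitz and Compound Symmetry last or deleted. Add, in the protocol or the SAP, that empirical (sandwich) standard errors apply whenever a structure other than unstructured is used. The second part is needed because Heterogeneous Toeplitz can itself understate the SE, to about 11% type I error under random-slope data.

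The cost is one sentence, best added before unblinding. Sandwich SEs displace small-sample degrees-of-freedom corrections, which is immaterial at this sample size.
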